
 • The difference in change from baseline in BP (SBP, DBP, and MAP) at Week 52 will be analyzed with a mixed model repeated measures (MMRM) approach with an unstructured covariance matrix to compare the difference in means between arms. The models will be fitted to scheduled BP data collected after baseline up to Week 52. Models will be run two times: 
 ○ On-treatment BP values only, excluding values collected during the stabilization period (Randomization date + 1 day to <Week 28). ○ On-treatment BP values only, including values collected during the stabilization period. 
The models will include factors for treatment, time, prognostic randomization stratification factors (see Section 10.10.2), baseline BP parameter and the baseline BP parameter by time and treatment by time interaction terms. Analyses will be done with the MIXED procedure in SAS, using the Kenward-Roger option to estimate denominator degrees of freedom and standard errors. For analyses using on- and off-treatment values, subjects who withdraw from the study before Week 52 are considered to be missing at random and in the analysis using

Secondary Safety Statistical Analyses: Blood Pressure

on-treatment values only, subjects who permanently discontinue randomized treatment before Week 52 are assumed to be missing at random.

- The difference in change from baseline in BP (SBP, DBP, and MAP) at the derived end of treatment (see Section 10.6.4) will be analyzed with an ANCOVA model including terms for treatment, prognostic randomization stratification factors (see Section 10.10.2) and the corresponding baseline BP parameter. This analysis will be performed using on-treatment BP values only.
- The number of on-treatment BP exacerbation events per 100 patient years will be calculated (see Section 10.6.4). Confidence intervals for the rate per 100 patient years will also be reported. For within group rates and the ratio of model estimated exacerbation rates, the point estimates, two-sided 95% confidence intervals, and one-sided p-value for the treatment group comparison will be obtained using a negative binomial model with treatment and the prognostic randomization strata as covariates and the logarithm of time on-treatment as an offset variable.

Model Results Presentation

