10.6.4.3. Blood Pressure Endpoints

Blood Pressure Endpoints
Pre- and Post- Dialysis BP

 For subjects undergoing dialysis in-clinic, both pre- and post- dialysis BP values will be measured. Unless otherwise specified, for summaries and analyses of BP values, the post-dialysis BP values for subjects undergoing dialysis in-clinic will be used.
End of Treatment BP Value

 See Section 10.6.1

Blood Pressure Endpoints
Mean Arterial Pressure (MAP)

 MAP = $[(2*DBP)+SBP]/3$
Blood Pressure Exacerbations

 BP exacerbations will be defined as (≥ 25 mmHg increase from baseline or SBP ≥ 180 mmHg or DBP ≥ 15 mmHg increase from baseline or DBP ≥ 110 mmHg) and grouped by type as follows: 
 BP exacerbations 
 SBP exacerbations 
 ≥ 25 mmHg increase from baseline or SBP ≥ 180 mmHg 
 SBP ≥ 180 mmHg and baseline SBP < 180 mmHg (including subjects with a missing baseline SBP) SBP ≥ 180 mmHg and baseline SBP ≥ 180 mmHg DBP exacerbations 
 ≥ 15 mmHg increase from baseline or DBP ≥ 110 mmHg 
 DBP ≥ 110 mmHg and baseline DBP < 110 mmHg (including subjects with a missing baseline DBP) DBP ≥ 110 mmHg and baseline DBP ≥ 110 mmHg
Notes:

 BP values used to assess BP exacerbations must be on-treatment (see Section 10.4.1), unless otherwise specified. BP values used to assess BP exacerbations can be scheduled or unscheduled. For visits where BP is measured in triplicate, the average of the 3 BP values will be used to assess BP exacerbations. For subjects who start in-clinic dialysis during the study, BP exacerbations identified using post-dialysis BP values will be used in summaries and analyses of BP exacerbations, unless otherwise specified. Subjects with multiple exacerbation events on the same calendar date for each type defined above are considered to have one exacerbation event for event counts by type. For example, a subject with a SBP and a DBP exacerbation on the same date would count in each of the SBP and DBP types, but would only count as one BP exacerbation event in the total BP exacerbation type.
Blood Pressure Exacerbation Event Date

 Date of BP exacerbation

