Category	Covariates and / or Subgroups	Summary of Demographics & Baseline Characteristics Note: Include 'Missing' categories, if applicable.	Subgroup Analysis for Co-primary MACE & Principal Secondary Safety Endpoints Note: Do not include 'Missing' categories.	Subgroup Analysis for Co-primary Hgb Endpoints Note: Do not include 'Missing' categories.
History of stroke	No, Yes, Missing	Yes	Yes	Yes
History of MI	No, Yes, Missing	Yes	Yes	Yes
History of cancer	No, Yes, Missing	Yes	Yes	Yes
History of heart failure	No, Yes, Missing	Yes	Yes	Yes
History of thromboembolic events	No, Yes, Missing	Yes	Yes	Yes
Hospitalization within 6 months prior to screening	No, Yes, Missing	Yes	Yes	Yes
Transfusion within 6 months prior to screening	No, Yes, Missing	Yes	Yes	Yes
Baseline iron use	No iron use IV iron use only Oral iron use only Other iron use only IV and oral iron use only IV and other iron use only Oral and other iron use only IV, oral and other iron use	Yes	No	No
Baseline SBP (mmHg)	Continuous covariate for change from baseline in SBP analysis, summary statistics of continuous values	Yes	No	No
Baseline DBP (mmHg)	Continuous covariate for change from	Yes	No	No

Category	Covariates and / or Subgroups	Summary of Demographics & Baseline Characteristics Note: Include 'Missing' categories, if applicable.	Subgroup Analysis for Co-primary MACE & Principal Secondary Safety Endpoints Note: Do not include 'Missing' categories.	Subgroup Analysis for Co-primary Hgb Endpoints Note: Do not include 'Missing' categories.
	baseline in SBP analysis, summary statistics of continuous values			
Baseline MAP (mmHg)	Continuous covariate for change from baseline in SBP analysis, summary statistics of continuous values	Yes	No	No
ACEI/ARB use at randomization	No, Yes	Yes	Yes	Yes
Phosphate binder use at randomization	Iron-based phosphate binders Calcium-based phosphate binders Non-calcium and non-iron based phosphate binders No phosphate binder use	Yes	No	No
Vitamin D use at randomization	No, Yes	Yes	No	No
History of cardiovascular disease	No, Yes	Yes	Yes	No
Beta blockers use at randomization	No, Yes	Yes	No	No
SGLT2i use at randomization	No, Yes	Yes	No	No
Statin use at randomization	No, Yes	Yes	No	No
Aspirin use at	No, Yes	Yes	No	No

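### The negative binomial model for on-treatment BP exacerbations omits baseline SBP and DBP: the comparison stays valid, but a little precision is given away

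*SAP*

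**What the plan says.** In SAP Section 8.2.2.2 (Blood Pressure, Model Specification), the exacerbation rate per 100 patient-years, the rate ratio, its 95% CI and the one-sided p-value come from a "negative binomial model with treatment and the prognostic randomization strata as covariates and the logarithm of time on-treatment as an offset variable". The strata are current ESA use and region.

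The other two BP models in that section do adjust for baseline. The MMRM for change at Week 52 includes the "baseline BP parameter and the baseline BP parameter by time and treatment by time interaction terms". The ANCOVA at end of treatment includes "the corresponding baseline BP parameter".

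Section 10.6.4.3 defines an exacerbation as "≥ 25 mmHg increase from baseline or SBP ≥ 180 mmHg or DBP ≥ 15 mmHg increase from baseline or DBP ≥ 110 mmHg", where the first limb is the systolic rise. The absolute limits count whatever the baseline. One listed subtype is "SBP ≥ 180 mmHg and baseline SBP ≥ 180 mmHg", and the subtype for a baseline below 180 is described as "including subjects with a missing baseline SBP".

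Section 2.2 places the endpoint among the secondary endpoints without multiplicity adjustment. Section 8.2.2.2 compares its one-sided p-value with 0.025 for nominal significance.

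**The concern.** A subject's Day 1 reading sets how far BP must rise before an exacerbation is counted. A Day 1 value that is low by chance brings the relative threshold closer to the subject's usual level. A Day 1 value near the absolute limit means that almost any reading at that level counts. Neither has anything to do with treatment, and in the planned model both stay in the overdispersion. The two continuous BP models remove the corresponding variation; the count model does not, and the SAP gives no reason for the difference.

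At stake is the width of the confidence interval for one of the listed secondary BP endpoints. Section 10.14 names raised BP as a risk of ESA treatment. Section 10.14.1.1 withdraws formal analysis from the ambulatory BP sub-study, so the formal BP comparisons now rest on Section 8.2.2.2.

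**Working it through.** **No figure to reproduce.** The SAP states no exacerbation rate, dispersion, BP standard deviation or power for this endpoint. Any size must come from assumed values.

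**How baseline enters the definition.** The systolic threshold is the lower of (baseline + 25) and 180, and the two meet at a baseline of 180 - 25 = 155 mmHg. The diastolic threshold is the lower of (baseline + 15) and 110, and the two meet at 110 - 15 = 95 mmHg. Below 155 the relative rule binds: a subject with baseline 120 must reach 145. Above 155 the absolute rule binds: a subject with baseline 170 needs a rise of only 10, and one at 180 or more needs none. The relation between baseline and event rate is therefore roughly V-shaped, and a straight line can capture only part of it.

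**Inputs to the simulation.** From the SAP: N = 4500 (Section 2.3 diagram), 1:1 allocation, the four criteria of Section 10.6.4.3, and the model with a log-time offset. Assumed: mean BP 136/75 mmHg, between-subject SBP SD 12-18, visit-to-visit SBP SD 10-14, baseline error 0.71 or 0.95 of the visit SD, subject drift SD 3 or 8, DBP SDs 0.6 times the SBP SDs, 4-23 visits at 11 per year, and a true effect of -1 mmHg SBP. There were 4-6 replicates per setting.

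**Linear baseline SBP and DBP added.** SE of the log rate ratio, with percent variance reduction = 100 × [1 - (SE ratio)²]:

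| Baseline error, drift SD | SBP SDs (between/visit) | SE without | SE with | Variance reduction |
|---|---|---|---|---|
| 0.71, 8 | 12/10 | 0.0547 | 0.0542 | 1.8% |
| 0.71, 8 | 15/12 | 0.0429 | 0.0427 | 1.0% |
| 0.71, 8 | 18/14 | 0.0353 | 0.0352 | 0.4% |
| 0.95, 8 | 12/10 | 0.0541 | 0.0526 | 5.2% |
| 0.95, 8 | 15/12 | 0.0430 | 0.0421 | 4.1% |
| 0.95, 8 | 12/14 | 0.0371 | 0.0347 | 12.9% |
| 0.95, 8 | 18/10 | 0.0522 | 0.0522 | 0.2% |
| 0.95, 3 | 12/10 | 0.0554 | 0.0530 | 8.2% |
| 0.95, 3 | 12/14 | 0.0364 | 0.0330 | 17.5% |

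The pattern fits the V shape. In a separate run (baseline error 0.71, drift SD 8), 17% of exceedances met an absolute limit only with SDs 18/10, where the linear gain vanishes. The share was 2% with SDs 12/14, where the linear gain is largest.

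**Linear plus quadratic terms.** Over a similar grid of 30 settings, the variance fell by 4.5-29%, with a median of about 10%. On the SE scale:
- 1 - √0.955 = 2.3% at the low end;
- 1 - √0.90 = 5.1% at the median;
- 1 - √0.71 = 15.7% at the high end.

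With SDs 18/10, baseline error 0.95 and drift SD 8, where linear terms gave nothing, the variance fell by 5.5%. A separate set of seven settings gave an SE reduction of 2-16%, and about 2-5% in six of the seven. Linear terms alone gave 0.3-16% there.

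**In sample-size terms.** An SE reduction of 2-5% equals 1/0.98² - 1 = 4% to 1/0.95² - 1 = 11% more subjects.

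**In confidence-interval terms.** Around a true ratio of 1, the upper 95% limit is exp(1.96 × SE). With SE 0.0430 it is 1.088. With a 5% lower SE (0.0409) it is 1.083.

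**The case against.** The strongest reply is that nothing here is an error. Randomization makes the unadjusted rate ratio valid, and the endpoint is nominal. The SAP's event endpoints (co-primary MACE, time to rescue, the CV composites, time to first transfusion) also adjust for treatment and stratification factors only. Section 10.10.1 lists baseline SBP as a "Continuous covariate for change from baseline in SBP analysis", which names no count model. On that view the exacerbation model follows the plan's own pattern for events, and the MMRM and ANCOVA are a different kind of model. All of this stands, and it is why the point concerns efficiency and not correctness. It does not explain why a covariate that helps define the event should be left out. MACE is not defined from a baseline reading; half of the exacerbation criteria are.

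A second reply is that the estimate is already precise and the gain may be trivial. That is partly right: as the working shows, the limits move only in the third decimal in a typical setting. Day 1 BP is also taken in triplicate (Section 10.2.1.1), which lowers baseline error and weakens regression to the mean. The low-gain rows in the table take baseline error as 0.71 of the visit SD, so its variance is about half the visit variance. If later visits are single readings and w is the within-sitting share, then 1 - (2/3)w = 0.5 gives w = 0.75. Three-quarters of visit-to-visit variance would then have to be noise within one sitting, which is favourable to the current model.

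Two limits remain. The simulations count scheduled readings only, whereas Section 10.6.4.3 also admits unscheduled ones. The SAP's mean imputation for continuous covariates (Section 7.2.2) belongs to a supportive MACE analysis, so it is a convention to borrow and not a rule already in force for main models.

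**Conclusion.** The point holds as a minor, nearly free improvement. The exacerbation model omits baseline SBP and DBP although two of its four criteria depend on them and the neighbouring BP models adjust for them. With linear plus quadratic terms the standard error of the log rate ratio would typically be about 2-5% lower (range about 2-16%). With linear terms only, the gain is close to zero in some settings. All of this rests on assumed BP variances, because the SAP supplies none.

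Three stronger readings are not supported:
- A reader might infer that every exacerbation is defined relative to baseline. Two criteria are absolute and apply even when baseline is already above the limit or is missing.
- A reader might infer that the comparison is biased, or that chance imbalance in baseline BP threatens it. Treatment is randomized, type I error is unaffected, imbalance is small at N = 4500 and already reflected in the interval, and the simulated estimates moved by only about 0.01 on the log scale.
- A reader might take the top of the range as the expected gain. Large gains appear in few settings, and nothing in the SAP shows that they apply to this trial.

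**What to change.** In Section 8.2.2.2, add baseline SBP and baseline DBP to the negative binomial model for on-treatment BP exacerbations, each with a linear and a quadratic term. For subjects with missing baseline BP, who can still have events through the absolute limits, impute the overall mean so that they stay in the model. The supportive expanded-covariate MACE analysis in Section 7.2.2 uses the same convention. Make the change before unblinding.

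The cost is a line or two of text and up to four more covariates; no new data are needed. The rate ratio becomes conditional on baseline BP, and the text should say at which baseline values the model-estimated rates per arm are evaluated.

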8.2.3. Exploratory Safety Analyses

8.2.3.1. Overview of Planned Exploratory Safety Analyses

Table 9 provides an overview of the planned exploratory safety analyses.

Table 9 Overview of Planned Exploratory Safety Analyses

Endpoint	Analysis Population	Absolute				Change from Baseline			
		Summary		Individual		Summary		Individual	
		T	F	F	L	T	F	F	L
BP and BP Medication Changes									
SBP, DBP and MAP by visit	ITT	Included with BP secondary analyses (Section 8.2.2)							
SBP, DBP, and MAP change from baseline to last record prior to change in BP medications ¹	ITT					Y			
Number of BP medications per subject	ITT	Y							

Endpoint	Analysis Population	Absolute				Change from Baseline			
		Summary		Individual		Summary		Individual	
		T	F	F	L	T	F	F	L
by visit ¹									
CFB in number of BP medications per subject by visit ¹	ITT					Y			
Number (%) of subjects who had no change, an increase or a decrease in dosage or number of BP medications from baseline by visit ¹	ITT	Y							
Lipid Parameters									
Lipid parameters by visit (TC, LDL-C, HDL-C)	ITT	Y	Y			Y	Y		
Renal Function									
Serum creatinine observed and CFB	ITT	Y	Y			Y	Y		
UACR observed and CFB	ITT	Y	Y			Y	Y		
N (%) transitioning to dialysis	ITT	Y							

NOTES:

- T = Table, F = Figure, L = Listing, Y = Yes display generated.
- Summary = Represents TFL related to any summaries (i.e. descriptive statistics) of the observed raw data.
- Individual = Represents FL related to any displays of individual subject observed raw data.

[1]: Summary will include on-treatment BP values or BP medications taken while the subject was on treatment only.

8.2.3.2. Planned Exploratory Safety Display Details*Blood Pressure*

The last on-treatment BP parameter change from baseline value (SBP, DBP, and MAP) recorded prior to the first change in BP medications will be summarized using mean, standard deviation, minimum, P25, median, P75, and maximum by treatment group. The first change in blood pressure medication occurs at the earliest time a new anti-hypertensive medication is administered or if the dose or frequency of an existing blood pressure medication is changed for any reason (increased, decreased, discontinued, or switched to another agent) in any anti-hypertensive medication, except medication records with frequencies of “Once only” and “PRN.”

Number of BP medications per subject while the subject was on treatment will be summarized using mean, standard deviation, minimum, P25, median, P75, and maximum for each scheduled visit by treatment group. Number of BP medications for each subject at baseline is defined as the number of medications taken on the day before randomized treatment start date. For end of treatment, it is defined as the number of medications taken on last non-zero dose date + 1 day. The number of BP medications at all other nominal visits is defined as the number of medications taken on the day of the visit.

Medication records with frequencies of “Once only” and “PRN” will be excluded from this summary.

Change from baseline in the number of BP medications per subject while the subject was on treatment will be summarized using mean, standard deviation, minimum, P25, median, P75, and maximum for each scheduled visit by treatment group. The number of BP medications at baseline, end of treatment and all other nominal visits will be defined as described in the previous paragraph. Medication records with frequencies of “Once only” and “PRN” will be excluded from this summary.

Additionally, the number and percentage of subjects who had no change, at least one change, an increase, a decrease or a switch in the dosage or number of BP medications from baseline while the subject was on treatment will be summarized for each scheduled post-baseline visit by treatment group (see Section 10.6.4 for details of classifying BP medication changes). Medication records with frequencies of “Once only” and “PRN” will be excluded from this summary.

Cumulative number of changes in on-treatment BP medications from baseline to Week 52 and End of Treatment will be summarized by treatment group. For all records except with frequencies “Once only” and “PRN,” the cumulative number of changes will be summarized using mean, standard deviation, minimum, P25, median, P75, and maximum. The number and percentage of subjects with no change and at least one medication change will be displayed excluding “Once only” and “PRN” records. For subjects with at least one change, the number and percentage of subjects for each reason (increase, decrease, and switch) will be displayed (see Section 10.6.4 for details of counting BP medication cumulative changes) by treatment group. Number and percentage of subjects for each reason of BP medication change will be displayed by treatment group. Cumulative number of changes in on-treatment BP medication from baseline to Week 52 and End of Treatment for “Once only” records only will be summarized using mean, standard deviation, minimum, P25, median, P75, and maximum (see Section 10.6.4 for details of counting BP medication cumulative changes) by treatment group. This display will be repeated for subjects who did not initiate dialysis during the study.

Number and percentage of subjects with at least one PRN record at baseline and on-treatment BP medication during the period from randomized treatment start date to Week 52 and End of Treatment will be displayed by treatment group.

Number and percentage of subjects with any BP medication taken at baseline (the day before randomized treatment start date) and any on-treatment BP medication during the period from randomized treatment start date to Week 52 and End of Treatment will be displayed by treatment group. This display will be repeated for subjects who did not initiate dialysis during the study.

Lipid Parameters

Lipid parameter values for this study include total cholesterol, LDL-C (direct) and HDL-C. These values are collected according to the schedule outlined in the Time and Events table (see Section 10.2.1). Lipid parameter values follow the derivation guidelines for laboratory values outlined in Section 10.6.4. The summaries described below will include summaries in both SI units and conventional units for each of the lipid parameters and will summarize log-transformed values.

Total cholesterol, LDL-C (direct), and HDL-C on-treatment values will be log-transformed and summarized using geometric mean, CV, minimum, P25, median, P75, and maximum for each scheduled visit by treatment group. Graphical summaries will be provided.

Percent change from baseline in log-transformed total cholesterol, LDL-C (direct), and HDL-C on-treatment values will be summarized using percent change geometric mean, 95% confidence interval, minimum, P25, median, P75, and maximum for each scheduled visit by treatment group. Graphical summaries will be provided.

Renal Function

Renal function parameters for this study include eGFR, serum creatinine and UACR. These values are collected according to the schedule outlined in the Time and Events table (see Section 10.2.1). Renal function parameter values follow the derivation guidelines for laboratory values outlined in Section 10.6.4. eGFR summaries were described in the additional secondary safety analyses section (see Section 8.2.2). The UACR summaries below will summarize log-transformed values.

Post-randomization serum creatinine values will be summarized using mean, standard deviation, minimum, P25, median, P75, and maximum for each scheduled visit by treatment group.

On-treatment UACR values will be summarized using geometric mean, CV, minimum, P25, median, P75, and maximum for each scheduled visit by treatment group.

Post-randomization serum creatinine change from baseline values will be summarized using mean, standard deviation, minimum, P25, median, P75, and maximum for each scheduled visit by treatment group.

On-treatment UACR change from baseline values will be summarized using percent change geometric mean, 95% confidence interval, minimum, P25, median, P75, and maximum for each scheduled visit by treatment group.

The number and percent of subjects transitioning to dialysis during the study will be provided by treatment group.

8.2.4. Adverse Event Safety Analyses

Adverse events will be coded using the Medical Dictionary for Regulatory Activities (MedDRA) coding dictionary.

The reporting of the CEC-adjudicated CV endpoint events has been described in Section 7.2, Section 8.2.1 and Section 8.2.2. However, AE summaries and analysis will also include the AEs and SAEs associated with the adjudicated events listed below:

- All-cause mortality (CV and non-CV mortality)
- Non-fatal MI
- Non-fatal stroke
- Hospitalization for HF
- Thromboembolic events (vascular access thrombosis, deep vein thrombosis, pulmonary embolism)
- Progression of CKD

For the purpose of AE summaries and analysis, the investigator-reported AE details will be used, regardless of the adjudication outcome of the event.

Adopting recommendations from the Pharmaceutical Research and Manufacturers of America (PhRMA) Safety Planning, Evaluation and Reporting Team (SPERT) [Crowe, 2009], the first two tiers of the three-tier system will be used for the evaluation of AEs to examine the level of statistical evidence for differences between treatment groups.

- Tier 1 events in this study are defined as treatment emergent AEs of special interest (AESI). Tier 1 events will include AEs which meet criteria for inclusion as an AESI (see Section 10.6.4). Statistical comparisons will be made to compare the number and % of AESIs between the treatment groups, using the CMH chi-square test. A nominal statistical association will be declared if the unadjusted two-sided p-value for an event is less than 0.05.
- Tier 2 events in this study are defined as the most common treatment emergent AEs (those occurring in $\geq 5\%$ of subjects in any treatment group). Tier 2 events are mutually exclusive of the Tier 1 AESI events. Any statistical comparisons for Tier 2 events will be made to compare treatment groups with multiplicity adjustment, using a CMH chi-square test, and the double false discovery rate (FDR, see Section 10.6.4) [Mehrotra, 2012]. The double FDR multiplicity procedure is designed to limit the number of false positive signals identified to no more than two-sided 10% (the false discovery rate).

Unless otherwise specified, all other AE and SAE summaries will include all AEs.

See Section 10.4.1 for AE treatment state definitions.

The adverse event safety analyses will be based on the Safety population, unless otherwise specified.

